## **16. Study termination and completion**

The study may be terminated at any time for safety concerns by the PI, DSMC, IRB, or other appropriate regulatory bodies. Otherwise the study will continue until 90 patients are enrolled who complete the Day 3 assessment and will be considered complete when all study assessments and analyses have been concluded.

## 17. Statistical methods

### 17.1. Overall plan for statistical analysis

After enrollment is complete, the REDCap dataset will undergo DCC cross-checks for quality and accuracy. The PI will review blinded data to identify errors which, if they exist, will be rectified by reference to paper CRFs or to the EMR. After quality checks are complete, the REDCap dataset will be closed and locked. The biostatistician will then perform an intent-to-treat analysis to determine the primary and secondary outcomes. The DSMO will have complete access both to the raw data and to the analytic code used by the biostatistician and will nominate a qualified monitor who will review this work for rigor. Once this is complete, the primary and secondary outcomes will be finalized. At this point, the locked data will be made available to the PI and other investigators for additional analyses. For all analyses,  $\alpha < 0.05$  will be considered statistically significant and two-sided testing will be performed. When death is a competing risk, Fine and Gray regression analyses will be performed.

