### **12.1. Randomization and blinding**

Randomization and data entry will take place through a secure, web-based system managed by the CUMC Data Coordinating Center (DCC) headed by [name]. This password-protected system is based on the Research Electronic Data Capture (REDCap) platform. The Research Nurse will use paper clinical research forms (CRFs) to document the initial screening process. When this information is entered into REDCap, the system will automatically generate a subject identifier and randomization code using 1:1:1 randomization in randomly permuted blocks of 6. This randomization code will be electronically communicated to the research pharmacy along with a separate key which will allow them to identify the random assignment. The Columbia Research Pharmacy will prepare the study intervention in indistinguishable semi-opaque fluid bags. Although inulin is readily soluble at the study doses, the opacity of these bags will eliminate any possibility that a small amount of precipitant might reveal the study assignment to the ICU nurses who deliver the intervention. Five drops of non-caloric flavoring syrup (McKesson Supply, Yonkers, NY, Product #570727) will be placed into the reconstituted inulin/placebo to prevent any possibility of accidental unblinding based on taste in patients who are alert. The patient, treating ICU team including the ICU nurse, and study team will remain blinded to each assignment until the completion of the trial, with the DCC preparing unblinded safety reports for the DSMO at pre-specified intervals.

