### 13.3.3. Long-term telephone follow-up

Telephone interviews will be conducted with subjects or their surrogates 3 months after ICU admission and again 6 months after ICU admission. In the event that subjects are still hospitalized, these interviews will be conducted at the bedside. Vital status will be ascertained and, to minimize loss of follow-up information, we will interview subjects or surrogates to determine (1) discharge location type (classified as home, short-term rehabilitation, or long-term rehabilitation including skilled care facilities), (2) hospital admission to non-CUMC facilities after ICU discharge, (3) physician office visits after ICU discharge, and (4) infections or other adverse events after ICU discharge. If there are non-CUMC hospital admissions or other healthcare

interactions, permission will be requested to obtain relevant records to determine the nature of infections and to assess for potential medium- to long-term AEs related to the study intervention. Among surviving subjects, the EQ-5D-5L (EuroQol 2009) will be used to determine health status across the domains of mobility, self-care, activity levels, pain, and anxiety/depression. Use of this highly validated instrument will facilitate standardization and generalizability of results and will provide preliminary data for post-ICU discharge monitoring for later phase trials. This instrument can be applied via telephone in 5 minutes and was recommended in 2017 for post-ICU assessment of overall well-being after a three-round modified Delphi process involving clinical researchers from over 16 countries, patients/caregivers, clinicians, and research funders. EQ-5D-5L responses have the potential to vary depending on whether answers are provided on patients versus surrogates, and therefore we will additionally assess post-ICU disability using Katz' Index of Independence in ADLs (Activities of Daily Living). Although focused on functional status rather than well-being, Katz' ADLs has been validated as an important patient-centered outcome across dozens of populations and unlike the EQ-5D-5L has high agreement between patients and caregivers.

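### Section 17.1 ties database lock and investigator access to the end of enrollment and not to the end of the 6-month follow-up, which leaves the late outcomes and the blinding promise unprotected

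*Combined protocol and SAP*

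**What the plan says.** Section 17.1 sets out one sequence. It begins: "After enrollment is complete, the REDCap dataset will undergo DCC cross-checks for quality and accuracy". During this stage, "The PI will review blinded data to identify errors". Then: "After quality checks are complete, the REDCap dataset will be closed and locked". The biostatistician analyses the primary and secondary outcomes, and a monitor nominated by the DSMO reviews the work. Release follows: "At this point, the locked data will be made available to the PI and other investigators for additional analyses".

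The end of enrollment is the only trial milestone in that sequence. Section 16 fixes it by the Day 3 visit: "the study will continue until 90 patients are enrolled who complete the Day 3 assessment".

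Follow-up runs well beyond that. Section 13.3.3 states: "Telephone interviews will be conducted with subjects or their surrogates 3 months after ICU admission and again 6 months after ICU admission". Section 14 lists 3 months and 6 months among the REDCap events, so these data sit in the database that is to be locked.

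On blinding, section 12.1 says that the "study team will remain blinded to each assignment until the completion of the trial". Section 16 says that the study "will be considered complete when all study assessments and analyses have been concluded".

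**The concern.** The Day 3 milestone suits the primary and secondary outcomes but not the additional ones. Section 10.3.4 compares infections between arms out to 6 months, section 10.3.9 compares 90-day mortality, and section 10.3.10 compares EQ-5D-5L and Katz ADL at 3 and 6 months. If 17.1 is carried out as its words run, the most recent enrollees still owe some of these data at the lock. Either the lock shuts those data out, or they are collected after investigators have received a dataset meant for between-arm comparisons.

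Both results matter. Truncation would fall on the last patients enrolled and thin out outcomes that are already small in a 90-patient trial. Collection by staff who may know the allocation would weaken the outcomes most open to judgement: interview answers, adverse events reported by telephone, and infections reconstructed from interviews and outside records.

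**Working it through.** **Step 1: how many patients are followed.** Inputs, from section 12 (Retention): 90 patients needed with a Day 3 sample, 11.3% mortality by Day 3, and no discharges by Day 3.

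90 / (1 − 0.113) = 90 / 0.887 = 101.47, rounded up to 102. This reproduces the plan's enrollment figure.

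**Step 2: how many are still in follow-up when enrollment ends.** The accrual time T is not given, so a range of 12 to 48 months is assumed, with even accrual. For an outcome due m months after ICU admission, the number enrolled in the last m months is 102 × m / T.

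| Assumed accrual T (months) | 6-month contact not due (102 × 6/T) | Day 90 not reached (102 × 3/T) | Day 30 not reached (102 × 1/T) |
|---|---|---|---|
| 12 | 51 (50%) | 25.5 | 8.5 |
| 24 | 25.5 (25%) | 12.75 | 4.25 |
| 36 | 17 (17%) | 8.5 | 2.8 |
| 48 | 12.75 (12.5%) | 6.4 | 2.1 |

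These are upper bounds for two reasons.

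- Deaths are not removed. With the 25% 30-day mortality of Cohort #1 (section 6.1), taken as an assumption for this population, the 6-month column becomes 51 × 0.75 = 38 at T = 12 and 12.75 × 0.75 = 9.6 at T = 48.
- No time is allowed for cleaning, lock, analysis and review. If these took an assumed 3 months, the number not yet at 6 months at release would be 102 × (6 − 3)/T, which is the Day 90 column: 25.5 at T = 12 and 6.4 at T = 48.

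If the lock waits for the last 6-month contact, every entry is zero.

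**Step 3: the passages side by side.**

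- 17.1: the stated trigger is the end of enrollment. There is one lock, then release to investigators for additional analyses. No staged lock is described.
- 12.1: the study team stays blinded until the trial is complete.
- 16: completion requires both assessments and analyses to be finished.

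A lock and release soon after enrollment ends would come before completion as section 16 defines it, and so would break 12.1. A lock after the last 6-month contact removes the follow-up problem but leaves a smaller inconsistency. Section 16 counts analyses as part of completion, yet 17.1 gives investigators the data in order to do further analyses, and sections 10.3.2 to 10.3.10 define these largely as between-arm comparisons. The wording needs alignment on either reading.

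**Step 4: which outcomes are exposed.**

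- Day 3 primary and secondary outcomes: not exposed, because enrollment stops only once 90 patients have completed Day 3.
- 90-day mortality: could be cut off by the lock, but it comes from the EMR and the death index and is little open to assessor bias.
- EQ-5D-5L, Katz ADL, telephone-reported adverse events and infections to 6 months: exposed both to truncation and to possible knowledge of allocation.

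**The case against.** A reader might infer that the plan releases unblinded data the moment enrollment closes, and that late outcomes will be lost or gathered by an unblinded team. The documents do not support that.

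- The opening words of 17.1 set an earliest point, not a date. Checks, lock, analysis and the monitor's review all come before release.
- 17.1 does not call the released data unblinded. That is an inference, though a fair one: the pre-lock data are described as blinded, and the later analyses compare arms.
- Other sections point to a late lock. Section 14.2 pairs the data lock with closure of the trial, section 15.3 intends blinding to last for the whole trial, and the release in 17.1 is for analyses that include 6-month outcomes. A lock after follow-up is the reading that best fits these sections.

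The consequences are also bounded. An MDR infection under section 10.3.4 needs a positive culture or molecular test and targeted treatment, which limits judgement. Quality of life is answered by patients or surrogates. The documents do not say who adjudicates infections. The largest count needs accrual within 12 months, whereas section 10.3.1 reports the enrollment rate for each 12-month period, which suggests a longer accrual.

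All of this stands, and it makes the matter a risk under one reading and not a stated plan. It does not supply the missing milestone. Because both main outcomes need only Day 3 data, locking soon after enrollment is a natural way to carry out 17.1 as written, and nothing in that section prevents it.

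**Conclusion.** The point holds in this form: 17.1 names the wrong milestone for the Day 30, Day 90, 3-month and 6-month outcomes, and read literally it conflicts with 12.1 taken together with section 16. The size is at most about 51 to 13 of 102 patients not yet at 6 months when enrollment ends. That range assumes even accrual over 12 to 48 months, no deaths removed and no time for cleaning, so the true number would be smaller. The conclusion about the trigger does not depend on these counts. The effect is confined to additional outcomes, chiefly the interviews, reported adverse events and late infections. The change should be made before the closing sequence begins, but it does not call the primary or secondary result into question.

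**What to change.** In 17.1, replace the trigger: the final lock, and release of allocation to the PI, the interviewers and those adjudicating infections, follow the last patient's 6-month contact. If Day 3 results are wanted earlier, add a separate Day 3 lock, analysed by the biostatistician and reviewed by the DSMO's monitor only, with allocation and arm-level results held back from everyone else until the final lock. A single clause moving the lock would be enough if no early result is needed.

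In 12.1 and section 16, define completion for blinding purposes as completion of all assessments, not of all analyses, so that investigators can carry out the additional analyses without breaching the text.

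The cost is about one paragraph of text and a delay of up to about 6 months before investigators see arm-level results. Sample size, visits and treatment are unchanged.

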### 17.2. Determination of the primary and secondary outcomes

Primary outcome: within-individual change in relative abundance of SCFA producers. 16S rRNA gene sequencing data will be processed using the QIIME platform with appropriate rarification and filtering. The primary analysis will be intent-to-treat, restricted to the subjects who complete the Day 3 assessment and contribute data. Within-individual change in SCFA producers will be calculated as Day 3 minus baseline relative abundance and an ANOVA or Kruskal-Wallis (KW) test (if skewed data) will be used to assess for differences across the three groups. If there is no significant difference between the low- and high-dose inulin arms, these arms will be combined for comparison against placebo in the final analysis using a two-sample t-test or rank-sum test. Although the primary analysis will be with the Day 3 samples, unadjusted and adjusted longitudinal data analysis will be performed using the generalized estimating equation approach with working independence correlation structure.

Secondary outcome: MDRO colonization. Subjects who culture positive from rectal swabs from Day 3 for MRSA, VRE, or a Gram negative with non-susceptibility to a third generation cephalosporin will be classified as MDRO colonized and all other subjects as not MDRO colonized. The proportion of patients who are MDRO colonized on Day 3 will be compared between intervention groups using a chi-squared test or Fisher's test. For this analysis, patients in the inulin arms will be combined if testing shows no significant difference between these inulin arms. Because baseline colonization status is likely to be an important predictor of Day 3 colonization status, we will test whether baseline MDRO colonization rates differ between intervention groups. If such a difference is observed, we will reanalyze Day 3 MDRO colonization with stratification according to baseline MDRO colonization (baseline MDRO colonized vs not colonized). Exploratory analyses will examine Day 7 MDRO colonization status and semi-quantitative culture data using ANOVA or Kruskal-Wallis testing. The difference in rates of Day 3 MDRO colonization will be taken as the effect size estimate for future trials.

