## 9.2. Rationale for the selection of duration and dose.

9.2.1. Rationale for duration. Inulin will be given for 7 days with the primary outcomes adjudicated after 3 days. The Day 7 data will be used to test whether an effect can be extended or whether a delayed effect is present. In our cohort data, 84/126 (67%) new infections occurred within 3 days and 97/126 (77%) within 7 days. This shows that any ICU-based intervention seeking to prevent infections must work quickly if it is to be effective. Meanwhile, our preliminary cohort data suggests that fiber can have an impact even within this short timeframe (Figure 3). A final assessment will be made on the day of hospital discharge in subjects who are to be discharged prior to Day 14.

9.2.2. Rationale for dose. In the ambulatory setting, inulin impacts SCFA producer levels at doses of 12 to 16 g/day, with biologic effects relevant for ICU patients (e.g., decreases in serum LPS and CRP). Approximately 16 g/day therefore represents the minimum dose at which an effect *might* be seen; this was selected for the low dose arm of the study. However, patients in these ambulatory studies were not critically ill and did not receive antibiotics. It is possible that inulin will have lesser effects in the ICU compared to the ambulatory setting, and logical to test higher doses. To select a maximum study dose, we referenced our own experience with dietary fiber in the prospective cohort and published tolerability data from ICU studies of inulin-like prebiotic fiber. In our prospective ICU cohort, 30 g/day was the maximum observed dose of dietary fiber, and was not associated with any intolerance. In published literature, O’Keefe *et al.* reported tolerance up to a maximum of 36 g/day wheat dextran in the ICU. We therefore selected 32 g/day for the high dose study arm because it lies between these values and is exactly double a dose with proven biologic activity.

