### 17.3. Power calculation and sample size

Primary outcome: within-individual change in relative abundance of SCFA producers. The study is powered to detect a difference in SCFA producer levels that is equal to or greater than the observed difference in SCFA producer levels from our prospective cohort (6.6% for high vs 3.7% low dietary fiber). The rationale for this is that inulin must be at least as impactful as mixed dietary fiber to be a viable therapeutic. The proposed sample size of 30:30:30 will yield 80% power to detect a minimum difference of 0.73 standard deviations (SD) comparing any one inulin arm to the placebo arm using a two-sided t-test with 0.05 significance level and assuming equal variance. If the inulin arms have similar changes in SCFA producer levels, they will be combined and the study would have 80% power to detect a minimum 0.63 SD for inulin compared to placebo at the .05 significance level. This sample size will also have 80% power to detect 0.33 SD differences among the 3 means versus the alternative of equal means using an F-test at the .05 significance level.

Secondary outcome: MDRO colonization. Power calculations were performed using the observed 42% rate of MDRO colonization in our prospective ICU cohort and 1:1:1 allocation to the intervention. Because this is an early phase study conducted with the expectation that promising results will be followed up by definitive larger studies, sample size calculations are based on one-sided testing with alpha .10 using a t-test based on the binomial distribution. Under these assumptions, a sample size of 90 patients will yield 80% power to detect a 20.4% or less rate of MDRO colonization on Day 7 with inulin, assuming that the two inulin arms are combined. If the inulin arms are not combined, there will be 80% power for a 17.3% or less rate of Day 7 MDRO colonization comparing any one inulin intervention arm vs placebo. The two-sided 95% confidence interval for the effect size estimate within the combined inulin arms would be 7.1 to 26.6% for an estimate centered on 15% and 10.8 to 32.3% for an estimate centered on 20%.

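### The primary analysis pools the two inulin doses whenever a 30 v 30 test is non-significant, and Section 17.2 names no placebo comparison if the doses differ

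*Combined protocol and SAP*

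**What the plan says.** For the primary outcome, the change in SCFA-producer abundance from baseline to Day 3, Section 17.2 sets out three steps.

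- First, "an ANOVA or Kruskal-Wallis (KW) test (if skewed data) will be used to assess for differences across the three groups".
- Second, the two doses are compared with each other, by a test that is not named.
- Third, given "no significant difference between the low- and high-dose inulin arms, these arms will be combined for comparison against placebo in the final analysis", a t-test or rank-sum test is used.

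Supportive work follows: "unadjusted and adjusted longitudinal data analysis will be performed using the generalized estimating equation approach with working independence correlation structure". The adjustment covariates are not listed.

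Section 17.1 sets one level for every analysis: alpha below 0.05 "will be considered statistically significant and two-sided testing will be performed".

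Section 17.3 gives 80% power for three different tests at 30:30:30, each at 0.05:

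- 0.73 SD, "comparing any one inulin arm to the placebo arm using a two-sided t-test with 0.05 significance level and assuming equal variance";
- 0.63 SD for the combined arms, with the condition worded as "If the inulin arms have similar changes in SCFA producer levels, they will be combined";
- a three-arm F-test: "This sample size will also have 80% power to detect 0.33 SD differences among the 3 means".

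Section 9.2.2 explains the low dose: "Approximately 16 g/day therefore represents the minimum dose at which an effect" might be seen.

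**The concern.** Three tests could each settle the primary outcome, and the text does not rank them. The words about the final analysis point to the pooled test, but only on the branch where pooling happens. On the other branch Section 17.2 names no comparison with placebo. The three-arm test is described as assessing differences, without a statement that it decides, opens the way to the later tests, or merely describes.

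The trigger is a separate weakness. Section 17.3 speaks of doses with similar changes. Section 17.2 replaces that with failure to reach significance at 30 v 30, which is not the same thing.

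At stake are the 0.05 level, which a data-dependent choice of test does not guarantee, and the reading of the result. If the low dose proves too low, which Section 9.2.2 leaves open, the doses will usually differ significantly and the placebo comparison would have to be chosen after the data are seen. If one dose truly has twice the effect of the other, the two will usually be merged into one average.

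**Working it through.** **Inputs.** 30 per arm, two-sided 0.05, 0.73 SD, 0.63 SD and 0.33 (Sections 17.1 and 17.3). No SD for the Day 3 change is given, so all effects are in SD units.

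**The plan's own figures reproduce.** The noncentrality for a t-test is d·√(n₁n₂/(n₁+n₂)).
- 30 v 30: 0.73·√15 = 2.83, power 79.4%.
- 60 v 30: 0.63·√20 = 2.82, power 79.6%.
- F-test (2 and 87 df), noncentrality 90·f² = 90·0.33² = 9.8: power 79.3%. This works only if 0.33 is Cohen's f.

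**The pooling trigger.** The largest observed low-v-high gap that is still non-significant is t(0.975, 58)·√(2/30) = 0.517 SD. The test has 28% power for a true gap of 0.365 SD and 79% for 0.73 SD.

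**The two-stage rule.** Simulation with normal data, equal variance and at least 400,000 trials per row. Entries are % of trials; means are placebo/low/high in SD.

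| True means | Arms pooled | Pooled test reached and significant | Pooled, else either dose v placebo at 0.05 | Same, gated by ANOVA | Three-arm test alone | Always pooled |
|---|---|---|---|---|---|---|
| 0/0/0 | 95.0 | 4.8 | 6.6 | 3.9 | 5.0 | 5.0 |
| 0/0/0.73 | 20.6 | 7.2 | 76.5 | 75.2 | 82.7 | 33.3 |
| 0/0.365/0.73 | 71.5 | 48.1 | 75.0 | 68.0 | 70.1 | 67.0 |
| 0/0.63/0.63 | 95.0 | 75.6 | 80.4 | 69.3 | 69.8 | 79.6 |

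If only the high dose is tested after a dose difference, null error is 5.7%. The extra error comes from selection. The 5.0% of null trials that reach the unpooled branch add 6.59 − 4.79 = 1.80 points, so about 36% of them (1.80/5.0) give a false positive. Rank tests on skewed, zero-heavy null data give the same error rates within about 0.1 point.

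With true effects of 0.365 and 0.73 SD, the pooled contrast estimates (0.365 + 0.73)/2 = 0.55 SD, about 0.18 SD from each dose's own effect.

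**Baseline as covariate.** Let k be the Day 3/baseline SD ratio and r their correlation. Relative to the change score, the adjusted variance is k²(1 − r²)/(k² + 1 − 2rk).
- k = 1, r = 0.5: 0.75/1 = 0.75.
- k = 0.5, r = 0.9: 0.0475/0.35 = 0.14.
- k = 1.5, r = 0.7: 1.1475/1.15 = 1.00.

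The documents give neither k nor r, so k from 0.5 to 1.5 and r from 0.3 to 0.9 are assumptions. Over that range the factor runs from 0.14 to 1.00. At 0/0.63/0.63 with equal SDs, the adjusted three-arm test has 87/82/77/72% power at r = 0.3/0.5/0.7/0.9. In the worst case it loses about half a point (69.3% v 69.8%). These figures are for raw-scale normal data only.

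**The F-test wording.** If 0.33 SD is read literally as the range between extreme arms, f is 0.33/√6 = 0.135 (evenly spaced) or 0.33·√2/3 = 0.156 (one arm apart), and power is 19% or 24%. Power of 80% needs f = 0.333, a range of 0.333·3/√2 = 0.71 SD (one arm apart) to 0.333·√6 = 0.82 SD (evenly spaced).

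**The case against.** The gap is smaller than Section 17.2 alone suggests. Section 17.3 sizes a single dose against placebo, and for MDRO colonization it states the uncombined branch outright. A reader might infer from the 7% figure that the trial would miss a high-dose-only effect. That holds only if Section 17.3 is ignored; with its comparison as fallback, power is 76.5%. This stands, but Section 17.3 is a power statement: it does not say which dose is tested or in what order, and it has no multiplicity rule.

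The weak trigger does not cost detection power in the scenarios where both doses work. At 0/0.365/0.73 the two-stage rule with fallback has 75.0% power, against 70.1% for the three-arm test. This also stands. The cost there is null error above 0.05 and a blurred dose estimate.

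A natural reading is that ANOVA comes first and gates the rest, which gives 3.9% null error. That is plausible but not written, and it lowers power at 0/0.63/0.63 to 69.3%.

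Section 9.2.2 does not predict that only the high dose works. It calls a lesser ICU effect possible and describes the high dose as double an active one. High-dose-only activity is one scenario among several.

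Under Section 17.1 the biostatistician determines the outcomes before the investigators receive the locked data. That limits investigator choice but does not replace a written rule.

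**Conclusion.** The concern holds. Section 17.2 pools on a test too weak to show similarity, leaves the unpooled branch without a named placebo comparison, and does not state the role of the three-arm test. With the comparison implied by Section 17.3, null error is about 6.6% (5.7% if only the high dose is then tested, 3.9% if gated by ANOVA) against the stated 0.05.

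The documents do not support several stronger readings:
- An error rate of 7.7% or more needs further routes to success, such as counting a significant ANOVA as well, which no section states.
- The power figures in Section 17.3 are not wrong; only the wording of the F-test figure misleads.
- The unadjusted change score is valid; it may leave precision unused.
- The trial is not invalid. It is an early-phase study, and the inflation is modest.

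The numbers assume 30 evaluable patients per arm, equal variances and normal data, with the rank check covering null error only. The objectives figure in Section 7 is not shown in the text available, so a rule stated only there would not have been seen.

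**What to change.** 1. Before unblinding, name one decisive primary test at two-sided 0.05 that does not depend on the low-v-high result. Either the three-arm test or an always-pooled inulin-v-placebo test cures the problem, and the choice is the sponsor's. Three-arm against pooled power is 70% v 80% if both doses work at 0.63 SD, and 83% v 33% if only the high dose works at 0.73 SD. A significant three-arm test does not say which dose differs or in which direction; the contrasts must carry that.
2. Remove the significance-triggered pooling. Report low, high and pooled differences from placebo with 95% confidence intervals in every case.
3. Add baseline SCFA-producer abundance as a covariate in the primary analysis. The target contrast is unchanged, although the estimate may shift with chance baseline imbalance. The size of the gain cannot be known from the documents. If skewed data are to trigger a rank or transformed version, write the trigger and the exact version in advance.
4. In Section 17.3, restate the F-test figure as Cohen's f = 0.33, about 0.71 to 0.82 SD between extreme arms.

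The cost is SAP wording and minor programming. No new patients, samples or assays are needed, because the change score already requires the baseline swab.
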